8.	CHANGES OF ANALYSIS FROM PROTOCOL	31
9.	APPENDIX	32
9.1	AESI and ECI definitions	32
9.2	Fraction of Inspired Oxygen (FiO2)	36
9.3	Imputation rules for missing or partial AE on concomitant medication	37
10.	REFERENCES	38

LIST OF ABBREVIATIONS

Abbreviation or special term	Explanation	
AE	Adverse Event	
AESI	Adverse Event of Special Interest	
ATC	Anatomic and Therapeutic Class	
AZ	AstraZeneca	
BMI	Body Mass Index	
BP	Blood Pressure	
BSC	Best supportive care	
CI	Confidence Interval	
CRP	C-reactive Protein	
CSP	Clinical Study Protocol	
CSR	Clinical Study Report	
CTCAE	Common Terminology Criteria for AEs	
CTMS	Clinical Trial Management System	
ECG	Electrocardiogram	
ЕСНО	Echocardiogram	
ECI	Events of Clinical Interest	
ECMO	Extracorporeal Membrane Oxygenation	
eCRF	Electronic Case Report Form	
EES	Efficacy Evaluable Set	
ICU	Intensive Care Unit	
iDMC	Independent Data Monitoring Committee	

IPD Important Protocol Deviation

KM Kaplan-Meier

MAP Mean Arterial Pressure

MedDRA Medical Dictionary for Regulatory Activities

mSOFA Modified Sequential Organ Failure Assessment

NG Nasogastric

P/F PaO₂/FiO₂

PK Pharmacokinetic

PKS Pharmacokinetic Analysis Set

PT Preferred Term

SAE Serious Adverse Event

SAS Safety Analysis Set

SD Standard Deviation

SOC System Organ Class

SoA Schedule of Activities

TEAE Treatment Emergent Adverse Event

WHO-DD World Health Organization-Drug Dictionary

AMENDMENT HISTORY

Date	Brief description of change
	N/A

1. STUDY DETAILS

This statistical analysis plan (SAP) contains a more detailed description of the analyses in the clinical study protocol (CSP). This SAP is based on version 1 of the CSP.

This study is being conducted to support the ongoing clinical development of acalabrutinib (CALQUENCE®)¹ in hospitalized COVID-19 patients. Because many COVID-19 patients may be unable to swallow capsules due to respiratory failure (eg, they may require endotracheal intubation for ventilator support and NG tube placement), it is important to have a clinically acceptable method to administer acalabrutinib (capsules) via NG tube. Furthermore, due to the acute illness of COVID-19 patients, many hospitalized patients are placed on high doses of PPIs or continuous H2-receptor antagonists to prevent stress ulcers. This study is designed to determine the PK, and safety and tolerability of acalabrutinib suspension, when coadministered with a PPI, in participants with confirmed SARS-CoV-2 infection requiring hospitalization due to respiratory failure (as defined in the table below) attributable to COVID-19 pneumonia and who have an NG tube in place.

1.1 Study Objectives

The objectives for this study and the corresponding endpoints/variables are shown in Table 1.

Table 1 Objectives and Endpoints

Objective	Endpoint/Variable	
Primary Objectives	Primary Endpoints/Variables	
To characterize the PK of acalabrutinib and its active metabolite (ACP-5862) following administration of acalabrutinib suspension, when coadministered with a PPI, in participants with COVID-19	Primary PK parameters for acalabrutinib and ACP-5862 include AUC _{12h} , AUC _{last} , and C _{max} . Additional PK parameters are described in the protocol.	
To assess the safety and tolerability of acalabrutinib suspension in participants with COVID-19 when administered in the presence of PPIs and BSC	Type, frequency, severity, and relationship to study intervention of any treatment-emergent AEs or abnormalities of laboratory tests, SAEs, or AEs leading to discontinuation of study intervention	

¹ CALQUENCE sis a trademark of the AstraZeneca group of companies.

Objective	Endpoint/Variable
Secondary Objective	Secondary Endpoints/Variables
To evaluate the preliminary efficacy of adding acalabrutinib suspension to BSC for treatment of participants with COVID-19	 Proportion of participants alive and free of respiratory failure at Days 14 and 28 Percent change from baseline in CRP (time frame: baseline, Days 3, 5, 7, 14, 28) Time to improvement defined as time to clinical improvement of ≥ 2 points (from first dose date) on a 9-point category ordinal scale, live discharge from the hospital, or considered fit for discharge (a score of 0, 1, or 2 on the ordinal scale), whichever comes first, by Day 28
Exploratory Objectives	Exploratory Endpoints/Variables

1.2 Study Design

Approximately 20 participants will be included to ensure at least 16 participants are evaluable. participants will receive acalabrutinib suspension (ie, acalabrutinib 100 mg suspension in COCA-COLA® delivered via NG tube) bid for 14 days (a maximum of 28 doses). In addition to receiving best supportive care (SOC).

To assess the effect of PPIs, all participants must be receiving treatment with a PPI at the start of the study. Treatment with a PPI can begin at any time prior to enrollment, provided participants have received PPI treatment for at least 24 hours prior to the first dose of acalabrutinib suspension. Any PPI is permitted, provided it meets the minimum equivalent daily dose of 20 mg rabeprazole. Participants must be on this dosage of PPI at the start of the study. They may be weaned off PPIs during the study if medically appropriate.

[figure not shown]
Blood samples for plasma PK assessment of acalabrutinib and its metabolite (ACP-5862) will be collected at pre-dose and 0.5, 1, 2, 4, 6, and 12 hours following treatment with acalabrutinib suspension as described in the table below. Note that the sample at 12 hours must be collected prior to the subsequent acalabrutinib dose (for trough PK sample).

Table 2 PK Visit and Description

PK Visit	Description	Rationale
PK Visit 1	First PK sampling will occur on Day 1 (ie, first dosing day for acalabrutinib suspension)	Allows an early assessment of acalabrutinib and ACP-5862 PK in participants receiving acalabrutinib suspension via NG tube
PK Visit 2	Second PK sampling will occur a minimum of 4 days after the start of PPI treatment, irrespective of the timing of NG tube placement and any time after 2 doses of acalabrutinib suspension have been given (ie, PK sampling can begin prior to the third dose, or anytime thereafter) PK Visit 2 can occur as early as Day 2 (if participant has been on a PPI for ≥ 4 consecutive days prior to receiving the third acalabrutinib dose), and up to Day 4 (if participant initiated PPI treatment 24 hours prior to receiving the first dose of acalabrutinib on Day 1)	PPI exposure must occur for 4 consecutive days to reach the maximum PPI on-target effect PK sample can commence at any point after the second dose of acalabrutinib suspension to ensure steady-state levels of the active metabolite and
PK Visit 3	Third PK sampling will occur 3 days after PK Visit 2, OR on the last day the participant receives acalabrutinib treatment, whichever comes first	Allows an additional opportunity to assess the steady-state PK of acalabrutinib and ACP-5862 PK following delivery of acalabrutinib suspension via NG tube

Safety assessments, including AE reporting, will be performed through 28 (\pm 3) days after the last dose of the acalabrutinib suspension.

The study design is illustrated in Figure 1.

Blood samples for plasma PK assessment of acalabrutinib and its metabolite (ACP-5862) will be collected at pre-dose and 0.5, 1, 2, 4, 6, and 12 hours following treatment with acalabrutinib suspension. Note that the sample at 12 hours must be collected prior to the subsequent acalabrutinib dose (for trough PK sample).

Note: PK Visit 2 can occur as early as Day 2 (if participant has been on a PPI for \geq 4 consecutive days prior to receiving the third acalabrutinib dose), and up to Day 4 (if participant initiated PPI treatment 24 hours prior to receiving the first dose of acalabrutinib on Day 1). See table 3 for more information.

bid = twice daily; PK = pharmacokinetic(s); PPI = proton-pump inhibitor.

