2. ANALYSIS POPULATION

2.1 Definition of Analysis Set

Four analysis sets are defined in this study. A summary of the analysis sets used for each outcome variable in provided in Table 3.

The analysis populations are defined in Table.

Table 3 Populations for Analysis

Population/Analysis set	Description
PK Analysis Set (PKS)	The PK Analysis Set will include all participants who received ≥ 1 dose of
	acalabrutinib and had ≥ 1 post-dose evaluable PK data point for
	acalabrutinib. The population will be defined by AstraZeneca, the
	pharmacokinetics, and the statistician prior to any analyses being
	performed.
Safety Analysis Set (SAS)	The Safety Analysis Set will include all participants who received ≥ 1 dose
	of study intervention
Efficacy Evaluable Set (EES)	The Efficacy Evaluable Set will include all participants who received ≥ 1
	dose of study intervention

PK = pharmacokinetic;

; PPI = proton-pump inhibitor.

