4.3 Analysis of Pharmacokinetics

The PK analyses will be performed at AZ Research & Development.

The plasma concentrations of acalabrutinib and ACP-5862 will be listed for all subjects and summarized by analyte, and nominal sample time for all subjects in the PKS. Summary statistics, including sample size (n), arithmetic mean (Mean), standard deviation (SD), coefficient of variation (CV%), standard error of the mean (SEM), minimum, median, and maximum will be calculated for all nominal concentration timepoints.

Excluded subjects will be included in the concentration listings, but will be excluded from the summary statistics and noted as such in the tables.

All BLQ values will be presented as "BLQ" in the concentration listings and footnoted accordingly. For the calculation of summary statistics, plasma acalabrutinib and ACP-5862 concentrations BLQ will be treated as zero prior to the first quantifiable concentration and as missing elsewhere.

Mean and individual concentration-time profiles for plasma acalabrutinib and ACP-5862 will be presented on linear and semi-log scales. Linear mean plots will be presented with and without SD.

Plasma acalabrutinib and ACP-5862 PK parameters will be listed and summarized by analyte and treatment for all subjects in the PKS. Summary statistics (n, arithmetic mean, SD, CV%, SEM, minimum, median, maximum, geometric mean [Geom Mean] and geometric CV% [Geom CV%]) will be calculated for plasma acalabrutinib and ACP-5862 PK parameters. Excluded subjects will be listed in the PK parameter tables, but will be excluded from the summary statistics and noted as such in the tables.

Individual plasma concentrations of acalabrutinib and ACP-5862 will be presented with the same level of precision as received from the bioanalytical laboratory. Individual PK parameters will be reported to 3 significant figures for individual parameters, with the exception of T_{max} , T_{last} , and $t^{1}/_{2}$, which will be presented with 2 decimal places, and C_{max} , which will be presented in the same precision as the bioanalytical data.

The level of precision for each concentration and PK parameter statistic will be as follows:

- minimum/maximum with the same precision as in individual data
- arithmetic mean, median and geometric mean with one more level of precision than minimum/maximum
- SD with one more level of precision than mean/median
- n will be presented as an integer
- CV% and geometric CV% will be presented to 1 decimal place.

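### Profiles taken after PPI weaning can enter the primary PPI-coadministered PK result unidentified, chiefly at PK Visit 3

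*SAP*

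**What the plan says.** - **Objective (SAP 1.1, Table 1).** The first primary objective is to characterise the PK of acalabrutinib and ACP-5862 "following administration of acalabrutinib suspension, when coadministered with a PPI, in participants with COVID-19".
- **PPI requirement (SAP 1.2).** Assessing the effect of PPIs is given as the reason for requiring one. At least 24 hours of PPI treatment must precede the first dose, at or above a minimum equivalent daily dose. The requirement is tied to entry: "Participants must be on this dosage of PPI at the start of the study". The next sentence reads: "They may be weaned off PPIs during the study if medically appropriate".
- **PK Visit 2 (SAP 1.2, Table 2).** "Second PK sampling will occur a minimum of 4 days after the start of PPI treatment", and after two acalabrutinib doses. The stated rationale is "PPI exposure must occur for 4 consecutive days to reach the maximum PPI on-target effect". If the visit is held as early as Day 2, the participant must have had at least 4 consecutive PPI days before the third dose.
- **PK Visit 3 (SAP 1.2, Table 2).** "Third PK sampling will occur 3 days after PK Visit 2, OR on the last day the participant receives acalabrutinib treatment", whichever comes first. No PPI condition is stated.
- **Analysis set (SAP 2.1, Table 3).** "The PK Analysis Set will include all participants who received ≥ 1 dose of" acalabrutinib and who have at least one evaluable post-dose concentration. The visible row does not mention PPI use.
- **Summary (SAP 4.3).** "PK parameters will be listed and summarized by analyte and treatment for all subjects in the PKS". Concentrations are summarised by analyte and nominal sample time.

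**The concern.** The objective names a condition, PPI coadministration, that the analysis never checks at the time of sampling. The entry rule protects PK Visit 1. After that the PPI may be withdrawn, and neither the Visit 3 rule, the visible PK set nor the summary rule asks whether it was. The study has one treatment, so summarising by treatment separates nothing.

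At stake is what the primary AUC12h, AUClast and Cmax describe. If some profiles were taken off PPI, the reported figure is a blend of two conditions with unstated weights. The SAP itself treats PPI duration as material, since it times PK Visit 2 around it. Leaving the choice open also means that the handling of such profiles could be settled after concentrations are known.

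**Working it through.** The SAP gives no figure to reproduce. The check is a reading of the rules, visit-day arithmetic, and an illustration of size.

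**1. When PK Visit 3 falls.** SAP 1.2 places Visit 2 between Day 2 and Day 4. Visit 3 is 3 days later: 2 + 3 = Day 5 to 4 + 3 = Day 7, or earlier if treatment ends first. Dosing runs for 14 days, so Visit 3 lies inside the period in which weaning is allowed.

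**2. Rule against rationale at PK Visit 2.** Take a participant who starts the PPI 24 h before dose 1. Four days (96 h) from PPI start is 96 − 24 = 72 h after dose 1, which is Day 4. If the PPI is stopped on Day 2, the clause that counts from PPI start is still met on Day 4, but the 4 consecutive days in the rationale are not. The two statements diverge for that participant.

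**3. Does another rule catch an off-PPI profile?**
- SAP 2.1: membership needs one dose and one evaluable concentration. The term evaluable is not defined by PPI use, and membership is decided per participant, whereas PPI status can change between visits.
- SAP 2.2: deviations can affect the PK set. Weaning is permitted, so it is not evidently a deviation.
- SAP 3.1: profiles or parameters are excluded for unquantifiable data, poor terminal fit or excess extrapolation, with no PPI criterion.
- SAP 4.3: no split by PPI status or PK visit is stated.

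**4. Size, by assumption.** Let f be the share of profiles off PPI and R the off-PPI/on-PPI exposure ratio. On the log scale the blended mean is (1 − f)·ln(GM) + f·ln(R·GM) = ln(GM) + f·ln(R), so the geometric mean is multiplied by R^f. SAP 1.3 gives 16 evaluable participants. R and the number weaned are assumed; the SAP gives neither.

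| R | 4 of 16 at one visit (f = 0.25) | 4 of 48, three visits pooled (f = 0.083) |
|---|---|---|
| 1.0 | 1.000 (0%) | 1.000 (0%) |
| 1.25 | 1.057 (+5.7%) | 1.019 (+1.9%) |
| 1.5 | 1.107 (+10.7%) | 1.034 (+3.4%) |
| 2.0 | 1.189 (+18.9%) | 1.059 (+5.9%) |

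At one visit with R from 1.0 to 2.0, 2 of 16 off PPI gives 0% to +9.1%. The SAP does not give the direction of a PPI effect either; a ratio below 1 would reverse the sign (0.5^0.25 = 0.84, or −16%).

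**The case against.** Several points on the other side have weight.

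- **PK Visit 2 is built around PPI exposure.** A reader might infer that Visits 2 and 3 equally ignore PPI use. The documents do not support that: the Visit 2 rationale and its Day 2 condition both call for 4 consecutive days. Only a wording gap remains there.
- **Part of the text is not visible.** SAP 2.1 announces four analysis sets and shows three, and the Table 3 footnote has a gap before its PPI abbreviation. Removed text may mention PPI. This limits confidence, but the visible PK set row and section 4.3, which govern the primary summary, do not.
- **Exclusion routes exist.** The PK set is settled before any analysis, and deviations are defined in a separate list that is not shown. One therefore cannot say that off-PPI profiles will be included, only that no stated rule keeps them out.
- **PK is descriptive.** There are about 20 participants and no power calculation, and concomitant medications are recorded and listed with dose and dates. A careful reader could trace off-PPI profiles through the listings. The primary summary would still not separate them.
- **Weaning by Day 5 to 7 may be rare.** SAP section 1 describes acid suppression as stress-ulcer prevention in acutely ill patients. Nothing in the SAP supports a large share weaned by then, or a link between weaning and clinical improvement.
- **Visit 3 has its own purpose.** Its rationale is steady-state PK through the NG tube. Requiring 4 full-dose PPI days there, as the only primary set, would add a condition the SAP never set.

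**Conclusion.** The gap is real and limited. Off-PPI profiles can enter the primary PK result unidentified, mainly at PK Visit 3. At Visit 2 the timing rule and its rationale need reconciling. Visit 1 is largely protected by the entry rule.

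A reader might infer that the primary PK result will be materially biased. The documents do not support that: the weaning rate and the PPI effect are both unknown, and the shift could be nil. On the assumed ratio of 1.0 to 2.0 it is 0% to +19% with 4 of 16 profiles off PPI at one visit, and 0% to +6% if three visits of 16 are pooled. These figures assume one common ratio and that weaned participants otherwise resemble the rest.

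This should be fixed, with moderate confidence. It is not a fatal flaw in a small descriptive PK study.

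**What to change.** In SAP 4.3, before concentrations are reviewed:

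1. Derive a PPI-status flag for each PK profile from the concomitant-medication dates and doses already recorded under SAP 3.5.2. State how a reduced PPI dose is classed. Treat status as unknown where the PPI stop date is missing or partial, because the imputation rules in SAP 9.3 can move a stop date past the sampling day.
2. Summarise the primary PK parameters, and the concentrations, by PK visit and PPI status.
3. Base the PPI-coadministered conclusion on profiles taken while on PPI. List and summarise off-PPI profiles separately.
4. Reconcile the PK Visit 2 timing rule with its 4-consecutive-day rationale, and say which of the two the flag follows.

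The cost is SAP wording, one derived variable and some extra table columns, with no new data collection. The downside is a slightly smaller n for the on-PPI summary at Visit 3. The weaning rule is not touched.

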1.3 Number of Subjects

Approximately 20 participants will be enrolled to have at least 16 evaluable participants. No formal power calculation is used for sample size determination. The sample size is chosen based on desire to gain adequate information while exposing as few patients as possible to the study procedure.

2. ANALYSIS POPULATION

2.1 Definition of Analysis Set

Four analysis sets are defined in this study. A summary of the analysis sets used for each outcome variable in provided in Table 3.

The analysis populations are defined in Table.

Table 3 Populations for Analysis

Population/Analysis set	Description
PK Analysis Set (PKS)	The PK Analysis Set will include all participants who received ≥ 1 dose of
	acalabrutinib and had ≥ 1 post-dose evaluable PK data point for
	acalabrutinib. The population will be defined by AstraZeneca, the
	pharmacokinetics, and the statistician prior to any analyses being
	performed.
Safety Analysis Set (SAS)	The Safety Analysis Set will include all participants who received ≥ 1 dose
	of study intervention
Efficacy Evaluable Set (EES)	The Efficacy Evaluable Set will include all participants who received ≥ 1
	dose of study intervention

PK = pharmacokinetic;

; PPI = proton-pump inhibitor.

2.2 Deviations

Protocol deviation is defined in a separate protocol deviation list. The important protocol deviations will be listed and summarized. None of the deviations will lead to subjects being excluded from the analysis sets described in section 2.1 (with the exception of the PK analysis set).

The need for additional sensitivity analysis due to protocol deviations will be determined following review of the protocol deviations ahead of database lock and will be documented prior to the primary analysis being conducted.

In addition to the above, other study deviations captured from the eCRF module for inclusion/exclusion criteria will be tabulated and listed. Any other deviations from monitoring notes or reports will be reported in an appendix to the CSR.

3. PRIMARY AND SECONDARY VARIABLES

3.1 Pharmacokinetic Variables

The PK of acalabrutinib and its active metabolite ACP-5862 in subjects with COVID-19 when administered with BSC is a primary endpoint and will be assessed by following PK parameters:

- Primary PK parameters: AUC_{12h}, AUC_{last}, and C_{max}.
- Secondary PK parameters:
 - Acalabrutinib and ACP-5862: $t_{1/2}$, t_{max} , and λ_z .
 - Acalabrutinib: CL/F and Vz/F.
 - Metabolite to parent ratio for C_{max}, AUC_{last}, and AUC_{12h}.

All PK parameters include in the protocol are listed in the Table 4 below, and are defined as appropriate for study design.

 Table 4.
 Non-Compartmental Pharmacokinetic Parameters to be Calculated

Parameter	Label in TFLs	Definition	Method of Determination
AUC _{0-t}	AUC0-t	Area under the concentration-time curve from time 0 to the time of the last observed non-zero concentration	Calculated using the Linear Trapezoidal with Linear Interpolation Method
$\mathrm{AUC}_{0 ext{-inf}}$	AUC0-inf	Area under the concentration-time curve from time 0 extrapolated to infinity	$AUC_{0-inf} = AUC_{0-t} + (C_{last}/K_{el})$ where C_{last} is the last observed non-zero concentration
AUC%extrap	AUC%extrap	Percent of AUC0-inf extrapolated	%AUC _{extrap} = $(1 - AUC_{0-t}/AUC_{0-inf}) \times 100$
C _{max}	Cmax	Maximum observed concentration	Taken directly from bioanalytical data
T_{max}	Tmax	Time to reach C_{max} ; if the maximum value occurs at more than one timepoint, T_{max} is defined as the first timepoint with this value	Taken from clinical database as the difference in the time of the blood draw associated with C _{max} and the time of study drug administration
T_{last}	Tlast	Time of the last measurable non-zero concentration	Taken from the clinical database as the difference in the time of the blood draw associated with the last measurable concentration and the time of study drug administration
Kel	Kel	Apparent first order terminal elimination rate constant	Calculated by linear least-squares regression analysis from a semi-log plot of the plasma concentration-time curve, using the maximum number of points in the terminal log linear phase (e.g., 3 or more non-zero plasma concentrations)
t ¹ / ₂	t1/2	Apparent first order terminal elimination half-life	$t1/2 = 0.693/K_{el}$
CL/F	CL/F	Apparent total plasma clearance after oral (extravascular) administration (calculated for acalabrutinib only)	$CL/F = Dose/(AUC_{0-inf})$

Parameter	Label in TFLs	Definition	Method of Determination
V _z /F	Vz/F	Apparent volume of	$V_z/F = Dose/(AUC_{0-inf} \times K_{el})$
		distribution during the	
		terminal elimination phase	
		after oral (extravascular)	
		administration (calculated for	
		acalabrutinib only)	

Pharmacokinetic concentration data will be collected as per the schedule of activities (SoA) in clinical study protocol (CSP). PK analysis will, where possible, be carried out using actual times recorded in the raw data. If actual times are missing, nominal times will be used. Nominal sampling times and best fit of the regression will be used for any interim PK parameter calculations. Plasma concentrations of study drug and its metabolite are used as supplied by the analytical laboratory for PK analysis. The units of concentration and resulting PK parameters will be presented as they are received for the analytical laboratory unless otherwise specified in the PK order form.

PK parameters will be derived using non-compartmental methods with Phoenix® WinNonlin® Version 8.1, or higher and/or SAS® Version 9.3 or higher. PK parameters will not be calculated for profiles with less than 3 consecutive postdose time points with quantifiable concentrations. The data from profiles with insufficient data to calculated the PK parameters will be included in the listing of concentrations but excluded from the concentration summaries for the affected analyte and treatment.

For the calculation of PK parameters, plasma concentrations below the limit of quantitation (BLQ) prior to the first quantifiable concentration will be set to zero and plasma concentrations BLQ after the first quantifiable concentration will be treated as missing.

If an entire concentration-time profile is not quantifiable, the profile will be excluded from the PKS.

The C_{max} and t_{max} will be derived directly from the plasma concentration-time profiles. In the case where multiple peaks of equal magnitude are present, the earliest t_{max} will be reported.

 K_{el} will be calculated by log-linear regression of the terminal portion of the concentration-time profiles for the derivation of regression-based parameters where there are sufficient data. The AUCs will be calculated using 'Linear up/Log down' method. Where appropriate, the AUC_{last} will be extrapolated to infinity using Kel to obtain AUC_{inf}. The CL/F will be determined from the ratio of dose/AUC_{inf}. The Vz/F will be determined from the ratio of CL/F/Kel. The MR parameters will be calculated after molar conversion. If $t^1\!/_2$ is estimated over less than three half-lives, the Kel related values will be flagged in the data listings but will be excluded from summary and PK statistical analysis.

An Rsq adj value of ≥ 0.8 indicate good fit of the log-linear regression. Any Kel with a Rsq_adj of <0.8 be flagged in the data listings along with the regression-based parameters and discussed in the CSR. The Kel and related PK parameters will be excluded from summary and PK statistical analysis.

The minimum requirement for the calculation of AUCs will be the inclusion of at least 3 consecutive quantifiable concentrations. Where there are only 3 quantifiable concentrations at least one of these should follow the peak concentration. Where %AUC_{extrap} is >10%, AUC_{inf} and derived parameter values will be flagged and excluded from descriptive and inferential statistics and discussed in the CSR.

